5.1 Timing of Analyses

The study databases will be locked to data entry 90 days following the last enrolled participant's final study interview. This allows for time to complete quality control queries while analyses are started. Any additional queries identified following the data lock will be addressed and any final query resolutions to the data will be hard-coded into the data management programs and documented in the code. Analyses described in this SAP will commence once the locked data set is created and will be completed during the final year of the study.

5.2 Analysis Populations

5.2.1 Intention to Treat (ITT) Population

All subjects who consented, were randomized into either arm, and completed the baseline interview are considered enrolled and comprise the ITT population. Participants who complete the informed consent, are randomized but do not complete the baseline interview will be excluded from analysis.

5.2.2 Per Protocol (PP) Population

All subjects who consented, enrolled, and were randomized into either arm and who completed the 12-month follow-up interview.

5.3 Covariates and Subgroups

5.3.1 Covariates

Potential covariates are listed in Table 2.

5.3.1 Subgroups

This is a multisite study consisting of two sites. The data will be pooled across sites to assess the primary and secondary outcomes. Randomization is stratified by site and cohort and they will be included in all analyses as influential covariates and interaction effects between each of site and cohort with treatment arm will be assessed. Additional post-hoc subgroup analyses may be performed as exploratory analyses.

5.4 Missing Data

The extent of missing data will be examined, and the patterns of missing data will be assessed for randomness. This will be accomplished in part by comparing participant characteristics of those who complete the 12-month survey and related instruments to those who do not, using the non-missing data from all participants. In addition to these checks for patterns of missingness, we will evaluate whether multiple imputation methods might be appropriate. We will analyze the data using both case deletion and multiple imputation approaches and compare the results from the two methods. Should the two approaches differ markedly, we will conclude that the data missingness did not occur completely at random and will perform additional sensitivity analyses prior to reporting the results that are the least sensitive to the observed pattern of missing data.

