3.5.3 Visit Windows

Participants are randomized, and hence considered enrolled, following completion of consent and the baseline interview. The 12-month follow-up assessment occurs within a 4-week window starting at 12 months post-baseline. After the 4-week window, participants will be considered lost to follow-up.

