3.6.2 Description of Other Measures

Table 2 lists other outcomes, covariates, potential mediators and moderators.

Table 2. Description of other potential covariates

Variable	Data Source	Data Type
Sociodemographics		
• Age	Baseline	Continuous
• Race	Eligibility Screener	Categorical
• Marital status	Baseline Interview	Categorical
• Income	Baseline Interview	Continuous
• Education	Baseline Interview	Categorical
• Speaks English	Baseline Interview	Categorical
• Access to internet	Baseline Interview	Categorical
• Access to a computer	Baseline Interview	Categorical
• Family in Albuquerque	Baseline Interview	Categorical
• Know neighbor's name	Baseline Interview	Categorical

Table 2. Description of other potential covariates

Variable	Data Source	Data Type
• Interaction with family in Mexico	Baseline Interview	Categorical

4 Sample Size

We will recruit a total of 240 participants through our two partner agencies that both have a large clientele with our target population. Sample size estimates accommodate 33% attrition. With the expectation that 100 participants will complete the study in each arm, the following minimum hypothesized changes in outcome measures will be detected with >80% power, assuming type I error $\alpha = 0.017$ for three primary outcome measures (one in each Aim):

1. An 8-point decrease in depression as measured by the CES-D for the Intervention arm, from baseline to 12 months, with at least a 6.5-point greater decrease than control participants (between arms effect size Cohen's $d = 0.43$ with $SD = 15$), as shown to be feasible in prior work.^{11,12}
2. Cohen's d effect size ≥ 0.33 comparing arms on the changes over time of the CD-RISC scores, indicating increased resiliency in the intervention arm as compared to the control arm.¹³⁻¹⁵
3. Decreased social isolation as measured by the MOS-SSS in the intervention arm as compared to the control arm over time with Cohen's $d \geq 0.5$ ($SD = 16$).¹⁶⁻¹⁸

5 General Analysis Considerations

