5.10.2 Primary Analysis

Unadjusted mean changes for depression, resilience, and social support scores over time will be calculated and compared between the study arms. Linear mixed models will be fitted to the measures with the primary independent variable of interest Study Arm. **Covariates will include** age, marital status, number of children, other family or close friend living in same location as participant, speaks English, employed, and health status. The interest will be in the interaction between time point and intervention arm. Least squares mean estimates for the changes over time and their 98.3% confidence intervals will be reported for each arm. Additionally, we will report the coefficient, its standard error, and p-value for the interaction between time point and intervention arm from the linear mixed model.

Should our data assumptions of normality not be met, appropriate transformations will be identified or alternative generalized linear mixed models with alternate distributions will be fit. Our reporting will still follow as described above. We may need to use the delta method to calculate confidence intervals for point estimates on the original instrument scale.

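### The only trigger for further missing-data analyses is disagreement between case deletion and multiple imputation, but the two can agree while both are biased

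*SAP*

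**What the plan says.** SAP 5.4 starts with a check on observed data, "comparing participant characteristics of those who complete the 12-month survey and related instruments to those who do not", and considers whether imputation is suitable. It then commits to two analyses: "We will analyze the data using both case deletion and multiple imputation approaches and compare the results from the two methods". The decision rule follows: "Should the two approaches differ markedly, we will conclude that the data missingness did not occur completely at random". In that event the team "will perform additional sensitivity analyses prior to reporting the results that are the least sensitive to the observed pattern of missing data". The size of a marked difference is not defined and the additional analyses are not named. The protocol has the same text in Section 11.0, under Statistical Analysis of Survey Responses.

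The primary analysis (SAP 5.10.2) is a linear mixed model: "The interest will be in the interaction between time point and intervention arm". There is one follow-up assessment (SAP 3.5.3): "The 12-month follow-up assessment occurs within a 4-week window starting at 12 months post-baseline". On the expected loss, SAP Section 4 says "We will recruit a total of 240 participants" and "Sample size estimates accommodate 33% attrition", with 100 completers expected per arm.

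Neither document plans a delta-adjusted, tipping-point, pattern-mixture or reference-based analysis.

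**The concern.** Case deletion and standard multiple imputation both take it that, given the observed data, women who leave resemble those who stay. They diverge mainly when dropout follows something observed, such as the baseline score, and there imputation already makes the correction. If women leave because they are doing worse than their baseline predicts, both methods can be wrong by the same amount. The comparison then shows nothing and the plan stops. With no outcome measured between baseline and 12 months, imputation has no interim score that could reveal a decline.

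The arms make unequal demands: weekly two-hour sessions for a year against bimonthly calls. Protocol 13.0 also allows removal for disruption in group sessions, which only intervention women attend. Loss related to outcome and differing by arm is therefore plausible, though not shown. At stake is whether agreement between two methods that share an assumption gets reported as evidence of robustness.

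**Working it through.** **Amount missing.** 240 recruited and 200 completing is 40/240 = 16.7%. A 33% loss from 240 leaves 240 x 0.67 = 161, about 80 per arm, so the stated 33% does not fit the SAP's other two figures. Both rates are used below.

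**Inputs from the documents.** CES-D SD 15, target difference 6.5 points, alpha 0.017 per primary outcome.

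**Assumptions not in the documents.** Baseline to 12-month correlation r = 0.5; log-odds of dropout rising by 1 per SD (odds x 2.72); random dropout in controls; imputation within arm from the baseline score only; case deletion as the difference in mean change among completers. At r = 0.5 the SD of change is 15 x sqrt(2 x (1 - 0.5)) = 15, so it does not matter whether the SAP's 15 refers to scores or to changes.

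**Step 1: dropout depends on the part of the 12-month score that baseline does not predict.** The residual SD is 15 x sqrt(1 - 0.5²) = 12.99. Let u be the standardised residual and p the fraction missing. Women stay with probability 1 - expit(a + u), with a set so that average dropout is p. The stayers' mean residual is m = E[u(1 - expit(a + u))]/(1 - p), by numerical integration.

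- p = 0.167: a = -1.90, m = -0.1465, bias = 12.99 x (-0.1465) = -1.90.
- p = 0.33: a = -0.85, m = -0.2765, bias = 12.99 x (-0.2765) = -3.59.

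Because u is unrelated to baseline, the stayers' baseline mean is undisturbed and case deletion carries the whole bias. The imputation line fitted to stayers has the right slope but an intercept wrong by the same amount, so imputation carries it too. The expected gap is zero.

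**Step 2: dropout depends on the raw 12-month score.** The stayers' mean standardised outcome is m and their mean standardised baseline is 0.5m. Case deletion has bias 15(m - 0.5m) = 7.5m. Imputation has bias 15(m - 0.5bm), where b is the slope among stayers (0.462 at 16.7%, 0.443 at 33%).

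- p = 0.167: -1.10 and -1.69, gap 0.59.
- p = 0.33: -2.07 and -3.23, gap 1.16.

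**Step 3: comparison of mechanisms.** Rows 1 to 4 come from the formulas above; the other rows are simulated (r = 0.5, 33% missing). The last column is the share of simulated trials with 120 per arm in which the gap exceeds one standard error of the arm difference. That standard error is about 15 x sqrt(2/100) = 2.1 with 100 completers per arm.

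| Dropout depends on | Missing | Case deletion bias | Imputation bias | Gap above 1 SE |
|---|---|---|---|---|
| Residual, intervention arm only | 16.7% | -1.9 | -1.9 | 0% |
| Residual, intervention arm only | 33% | -3.6 | -3.6 | under 1% |
| Raw score, intervention arm only | 16.7% | -1.1 | -1.7 | 0.2% |
| Raw score, intervention arm only | 33% | -2.1 | -3.2 | 6 to 10% |
| Raw score, opposite directions by arm | 33% | -4.2 | -6.5 | 49% |
| Raw score, same in both arms | 33% | 0.2 | 0.2 | about 1% |
| Baseline score, intervention arm only | 33% | +1.9 | about -0.1 | 35% |

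In the last row imputation is already essentially unbiased, yet the alarm is far louder than in the first four, where bias remains. If both analyses adjust for baseline, the large-sample gap is at most 0.13 under every mechanism tried, and the bias remains.

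**Step 4: sensitivity to r.** For r from 0.3 to 0.7, holding the SD of change at 15, the Step 1 bias runs from -1.8 to -2.1 at 16.7% and from -3.4 to -3.8 at 33%.

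**The case against.** A reader might infer that the two methods always agree when dropout depends on the unseen outcome. That is not so. When dropout follows the raw score, its correlation with baseline opens a gap, and with heavy loss in opposite directions by arm the gap is often visible. When the dependence is the same in both arms, the arm difference is almost unbiased. The exact zero in Step 1 follows from choosing a mechanism unrelated to the only imputation variable.

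The imputation model is not specified in the SAP. Attendance and reasons for leaving are to be recorded. If dropout acted through attendance and attendance entered the imputation, much or all of the bias could go, and the two methods would then differ. If dropout acted on the outcome directly, bias would remain.

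A reader might also infer that the SAP treats agreement as proof that missingness is harmless. It does not say so. It draws only the reverse inference, from disagreement to data not missing completely at random, and that inference is reasonable. The completer comparison and the disposition summary with reasons (SAP 5.6) add information, although neither leads to any further analysis.

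Finally, stopping sessions is not the same as missing the 12-month survey. The survey and hair sample are paid separately from sessions in both arms, and controls are offered the intervention afterwards. The documents therefore do not support any particular dropout mechanism, its direction, or a specific false-positive rate. If women doing better were the ones to leave, the sign would reverse and a benefit would be hidden.

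What stands is that disagreement is the only stated trigger, and no planned analysis relaxes the assumption that both methods share.

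**Conclusion.** The point holds in limited form: agreement between case deletion and multiple imputation is not evidence against outcome-dependent dropout, and under SAP 5.4 such agreement ends the enquiry. Under the stated one-arm mechanism both methods are off by about 1.9 CES-D points at 16.7% missing and about 3.6 at 33%, which is 29% and 55% of the 6.5-point target (1.9/6.5 and 3.6/6.5). These sizes depend on the assumed slope, correlation and imputation model, and on which attrition figure is right. They show what the rule could miss and do not predict bias in this trial. That the two methods can agree while both are wrong does not depend on the particular values. The primary analysis itself is not invalidated; the gap is in the sensitivity plan and should be closed.

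**What to change.** In SAP 5.4, and in the matching protocol text, stop using agreement or disagreement of the two methods as the trigger. For the three primary outcomes, always run one pre-specified delta-adjusted multiple imputation:

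- Name the variables in the imputation model.
- Shift the imputed 12-month scores in the unfavourable direction, separately in each arm, over a stated grid. One example is 0 to 1 SD: 15 points for CES-D, 16 for MOS-SSS, and the observed SD for CD-RISC.
- Report the arm difference and its 98.3% confidence interval across the grid. Where a primary result is significant, also report the tipping point. The grid remains informative for a null result.

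A range of 0 to 1 SD is wide enough to be useful. A shift in one arm moves the estimate by the shift times the fraction missing: 15 x 0.167 = 2.5 points, or 15 x 0.33 = 5.0 points. It also covers the Step 1 example, where leavers average 1.90/0.167 = 11.4 points worse than comparable stayers at 16.7% missing, and 3.59/0.33 = 10.9 at 33%.

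Reconcile the 33% with 240 recruited and 200 completing, since this sets how much missing data can matter. The cost is a few lines of SAP text and standard code on data already held. The downside is one more table, which may show the result to be less robust.

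### SAP 5.4 designates no primary missing-data method, so the reported primary result can be chosen, on undefined criteria, after the results are seen

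*SAP*

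**What the plan says.** SAP 5.4 leaves the status of imputation open: "we will evaluate whether multiple imputation methods might be appropriate". It then commits to two methods: "We will analyze the data using both case deletion and multiple imputation approaches and compare the results from the two methods". The trigger for going further is a marked difference: "Should the two approaches differ markedly, we will conclude that the data missingness did not occur completely at random". In that case further sensitivity analyses, not described, come before "reporting the results that are the least sensitive to the observed pattern of missing data". The protocol repeats this text under Statistical Analysis of Survey Responses.

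SAP 5.10.2 gives the model: "Linear mixed models will be fitted to the measures with the primary independent variable of interest Study Arm". It gives the contrast: "The interest will be in the interaction between time point and intervention arm". It also lists covariates and sets 98.3% intervals. It does not mention missing data or an analysis set.

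SAP 5.2 defines two populations. For ITT: "All subjects who consented, were randomized into either arm, and completed the baseline interview are considered enrolled and comprise the ITT population". The per-protocol set is restricted to women "who completed the 12-month follow-up interview". Neither set is assigned to the primary analysis; only the safety analysis (5.15) is tied to ITT.

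**The concern.** A primary analysis should yield one result per outcome that can be identified before the data are seen. Here the last step, which result to report, depends on how the results compare and on a judgement of sensitivity that has no metric. Even when the two methods agree, nothing says which one supplies the reported estimate and p-value.

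Two things are at stake. One is the error rate: each primary outcome is tested at 0.017 to protect the family of three, and a choice made after seeing results can erode that. The other is bias. Completer-only analysis remains a candidate for the reported result. The intervention arm is asked to attend weekly two-hour sessions for a year while controls receive bimonthly calls, so dropout that differs by arm is plausible.

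**Working it through.** **1. Is a default named anywhere?** Set side by side:

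| Place | What it fixes | What it leaves open |
|---|---|---|
| SAP 5.4 and protocol statistical section | Both methods are run and compared | Which is primary; threshold for disagreement; measure of sensitivity; imputation model and number of imputations |
| SAP 5.10.2 | Linear mixed model, time-by-arm contrast, covariates, interval level | Missing-data method; analysis set |
| SAP 5.2 | ITT and per-protocol definitions | Which one the primary analysis uses |
| SAP 3.4.2 | Reports masked as Arm A and Arm B | Masking ends when the final analysis is performed, which is when 5.4 operates |

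No default is named.

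**2. The plan's own figures.** SAP 4 gives alpha 0.017 for three primary outcomes: 0.05/3 = 0.0167, so this reproduces. It also gives 240 recruited, 100 completing per arm and 33% attrition. These disagree: 1 − 200/240 = 16.7%, while 240 × 0.67 = 160.8, about 161 completers. I therefore take 17% to 33% as the range for missing 12-month data. Either end is enough for the choice of method to matter.

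**3. Upper bound on type I error.** Let Z1 and Z2 be the test statistics of two analyses of the same outcome, standard normal under the null with correlation ρ. The documents do not give ρ; I assume 0.80 to 0.95. The two-sided critical value is c = Φ⁻¹(1 − 0.017/2) = 2.387. If the more favourable analysis is always reported,

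P(reject) = 1 − P(|Z1| < c and |Z2| < c).

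Suppose instead that one analysis is the default and a switch is allowed only when |Z1 − Z2| > g, still towards the more favourable result:

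P(reject) = P(|Z1| > c, or both |Z1 − Z2| > g and |Z2| > c).

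The values of g are my assumed readings of a marked difference.

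| ρ | Always the more favourable | Switch if gap > 0.5 | Switch if gap > 1 |
|---|---|---|---|
| 0.80 | 0.028 | 0.025 | 0.021 |
| 0.90 | 0.025 | 0.021 | 0.018 |
| 0.95 | 0.023 | 0.019 | 0.017 |

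At ρ = 0.95 a gap above 1 occurs in about 0.2% of null trials: 2[1 − Φ(1/√0.1)] = 0.0016.

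**4. Choice versus bias.** This is a null simulation of change scores: 120 per arm, 4,000 runs, 20 imputations, baseline-to-12-month correlation 0.5 or 0.7, missingness 1/6 or 33%. With two time points and completers only, the time-by-arm contrast is a comparison of change scores (the listed covariates are left out here). In the missing-at-random scenario, dropout depends on baseline in opposite directions in the two arms and on one prognostic auxiliary variable. All of these settings are assumptions. Rejection rates at 0.017:

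| Dropout | Case deletion | Imputation, fixed in advance | Smaller p of the two |
|---|---|---|---|
| Completely at random | 1.4–2.0% | 1.4–2.1% | 1.7–2.6% |
| Arm-dependent, at random | 4.2–14.7% | 1.7–1.9% | 4.8–15.6% |

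Monte Carlo error near 1.7% is about 0.2 points. Under arm-dependent dropout the excess is almost all bias in case deletion. Choosing adds only 0.6 to 0.9 points to it (for example 4.8 − 4.2 = 0.6).

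**The case against.** The strongest reply is that 5.4 is not a licence to pick the best p-value. Its criterion is insensitivity to missingness, it applies only after marked disagreement, and further analyses must come first. This stands. A reader might infer that alpha is really 0.028, or that the rule was written to favour a positive result, especially as protocol section 9.0 reports an arm comparison at the end of Y2 and the SAP is dated June 23, 2024. The documents do not support either inference. What they show is undefined discretion, and the figures in step 3 are ceilings.

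Four other stronger readings also fail:

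- **That the whole primary analysis is open.** SAP 5.10.2 fixes the model, contrast, covariates and interval level. The missing-data method and the analysis set are what is open.
- **That agreement between the two methods is taken as proof of no bias.** SAP 5.4 draws a conclusion only from disagreement. It remains true that the two can agree and both be biased if dropout depends on unseen 12-month scores.
- **That a not-at-random check is ruled out.** The unnamed extra analyses could include one. None is specified, and they run only if the two methods disagree.
- **That women with baseline data alone are certainly dropped.** SAP 5.4 does not define case deletion, and a mixed model can keep these women. The SAP does not say that it will.

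The Arm A/Arm B masking deserves credit, but it ends at the stage where this choice is made.

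**Conclusion.** The concern holds in this form: no missing-data method or analysis set is designated as primary, the selection terms are undefined, and the choice is made on final-analysis results for three alpha-controlled outcomes. The text check alone establishes this, and it does not depend on the simulation.

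The size is conditional. Type I error per outcome can rise from 0.017 to at most 0.023–0.028 if the more favourable of two analyses is always reported and ρ is 0.80 to 0.95. Because the stated criterion is a different one, the true inflation is likely smaller. It nearly vanishes if a switch needs a large gap and the two statistics are highly correlated, although that calculation assumes a default that the SAP does not name. The larger exposure is that case deletion can become the reported result. If dropout depends on baseline score and arm, it is biased whoever makes the choice. How strong such dropout will be cannot be known from the documents.

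This should be corrected before the arms are unmasked for the final analysis.

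**What to change.** Replace the reporting rule in the last sentence of SAP 5.4, and the matching protocol text, with wording such as:

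> The primary result for each primary outcome is the likelihood-based linear mixed model of section 5.10.2 fitted to all ITT women with any outcome data (baseline-only records retained). Complete-case, multiple-imputation and delta-adjusted analyses (by arm, over a range of deltas fixed before unblinding) are sensitivity analyses, and all are reported regardless of result.

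The delta range must be written down at the same time; otherwise one undefined choice replaces another. A likelihood-based model still loses records with missing covariates, so one sentence on how those are handled would complete the change.

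The cost is wording in two documents, one extra sensitivity run, and the loss of discretion over which result is reported. No new data are needed. With the method fixed in advance, the nominal level for each outcome stays at 0.017.
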